TRIAL POPULATION	
Children with cystic fibrosis on highly effective modulator therapy (either ivacaftor or elexacaftor–tezacaftor–ivacaftor (ETI)) under the care of the Royal Children’s Hospital.
 
Members of the RCH CF MDT

DESCRIPTION OF SITES	The Royal Children’s Hospital (single site)
DESCRIPTION OF INTERVENTIONS	
Intervention group participants will be asked to complete a symptom survey twice a week. Over the course of ensuing 12-months, if the system detects a pulmonary exacerbation is present, families will be asked to complete the symptom survey on a daily basis and will receive an automated treatment plan sent via the electronic medical record informing them of changes to their child’s treatment plan. Control group participants will receive usual care for their child’s CF at RCH which typically involves 4 outpatient clinics per year.

TRIAL DURATION	It is estimated that the trial will be completed in 18 months.
PARTICIPANT DURATION	Participants will be involved in the study for approximately 14 months, including the intervention period of 12 months and baseline and final semi-structured interviews.

GLOSSARY OF ABBREVIATIONS

ABBREVIATION	TERM
CF	Cystic Fibrosis
CFTR	Cystic fibrosis transmembrane conductance regulator
FEV1	Forced expiration in the first minute
CFQ-R	Cystic fibrosis questionnaire revised
ETI	Elexacaftor/tezacaftor/ivacaftor
RCH	Royal Children's Hospital
EMR	Electronic medical record
TGA	Therapeutic goods association
MDT	Multidisciplinary team
QOL	Quality of life
LOS	Length of stay
SPSS	Statistical Package for the Social Sciences

INVESTIGATOR AGREEMENT

I have read the protocol entitled “Remote symptom monitoring and automated treatment plans in children with Cystic Fibrosis”.

By signing this protocol, I agree to conduct the clinical trial, after approval by a Human Research Ethics Committee or Institutional Review Board (as appropriate), in accordance with the protocol, the principles of the Declaration of Helsinki and the good clinical practice guidelines adopted by the TGA [Integrated Addendum to ICH E6 (R1): Guideline for Good Clinical Practice E6 (R2), dated 9 November 2016 annotated with TGA comments].

Changes to the protocol will only be implemented after written approval is received from the Human Research Ethics Committee or Institutional Review Board (as appropriate), with the exception of medical emergencies.

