1.3. Expected duration of study

Recruitment: 2 months

Intervention and follow period for participants: 12 months

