This will be a pilot randomised, non-blinded, single center trial in children with CF attending the RCH on highly effective modulators. The study will compare usual care to an intervention arm, with the intervention being the new remote symptom monitoring and automated treatment plan model of care.

Participants:

Participants will be children with a confirmed diagnosis of Cystic Fibrosis under the care of RCH, on a highly effective modulator (ETI or ivacaftor) and their caregiver. Participants will be included in the study only if they meet all of the inclusion criteria and none of the exclusion criteria.

Inclusion criteria:

- Diagnosis of Cystic Fibrosis
- On ETI or ivacaftor for a minimum of 2 weeks
- Clinically stable without antibiotic treatment for a pulmonary exacerbation in 2 weeks prior to consent
- Attending RCH CF clinic
- Able to complete home spirometry (standard of care for all children with CF >5 years at RCH CF clinic)
- Sufficient English to complete a survey
- Access to a smart phone to access remote symptom monitoring surveys

Exclusion criteria:

- Participants not signed up or not willing to sign up to the RCH Portal (note that 80% of RCH CF patients are already signed up to the portal)
- Participants who do not have access to a smartphone or computer on a daily basis
- Participants who do not have access to a home spirometer for lung function purposes
- Participants will be excluded from the study for technological access reasons such as lack of access to the RCH Portal and IT equipment as this is the basis of the intervention.

Sample:

Although this is a randomised controlled trial it is a pilot and currently there is no known sample size in the literature relating to a pilot trial. However, we will aim to include a minimum of 30 participants in the study in line with other pilot trials conducted by CI [name] [27]. We believe this will give us sufficient data on the feasibility and acceptability of the new model of care and potential effectiveness. If the intervention is feasible and acceptable the outcome data, which can be collected with minimal burden on participants and resources, will be crucial to inform sample size calculations for fully powered RCTs.

Study Name: Acceptability, feasibility and impacts of remote symptom monitoring and automated treatment plans in children with Cystic Fibrosis (CF) on highly effective modulators: a pilot randomised controlled trial.

Protocol Number: 91117

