Participants in the control arm will receive usual which consists of quarterly CF clinic visits and more urgent visits triggered by telephone calls from families concerned about their child's clinical status. This model of care relies on the participant/caregiver contacting the CF team if they notice a change in their symptoms.

Questionnaires

All online questionnaire links will be sent to participants via the portal.

Screening questionnaire:

A once off screening questionnaire will be linked to the initial study letter for participants to fill out prior to accessing the PICF and consent forms (Appendix 2).

Baseline:

Demographic questionnaire and data collection

A baseline demographic survey will be sent to all participants after online consent is gained (Appendix 4). Patient demographic and baseline data will also be collected via the EMR (Appendix 11)

Cystic Fibrosis Questionnaire- R (CFQ-R)

The CFQ-R (Appendix 12) is a validated questionnaire used to assess the health-related quality of life of people with CF of all ages [30]. It contains five generic domains, four specific domains, three

symptom scales and an overall health perception scale. It takes approximately 10 minutes to complete and can be self-administered.

EQ-5D-Y

The EQ-5D-Y (Appendix 13) is a validated survey assessing quality of life in a range of populations including CF [31]. It is a five-dimension survey encompassing mobility, looking after myself, doing usual activities, having pain or discomfort and feeling worried, sad or unhappy. It takes approximately 3 minutes to complete

3, 6 & 12 month follow up survey

A follow up survey will be sent to both the intervention and control group at 3, 6 and 12 months and will ask about number of pulmonary exacerbations, and data for health economics evaluation (e.g. time off work, travel costs) and information relating to burden of trial (Appendix 10)

At 12 months the *CFQ-R* and *EQ-5D-Y* will be completed also.

Procedures:

Spirometry

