5 SAFETY MONITORING AND REPORTING

Adverse events (non-serious and serious) will be captured from the time of first administration of the intervention until conclusion of the intervention and all events will be followed until resolution or stabilisation.

Risks:

Risk/Benefit assessment

Known potential risks

- Increased burden of care to families by having to fill out the symptom surveys twice a week
 - o Survey will take approximately 3 minutes to fill out each time
- Participants not filling out the survey and therefore not gathering enough data to assess feasibility/effectiveness
- Increased workload for CF team without extra funding
 - o The pilot allows patients and families to directly contact the CF team which may increase contacts

Study Name: Acceptability, feasibility and impacts of remote symptom monitoring and automated treatment plans in children with Cystic Fibrosis (CF) on highly effective modulators: a pilot randomised controlled trial.

Protocol Number: 91117

Version & date: version 2, 28.10.2022

- The pilot may identify more pulmonary exacerbations compared to usual care which may increase contacts with CF team
- Underestimating/overestimating pulmonary exacerbations in patients leading to changes in treatment
 - Underestimating: the system may miss small exacerbations where families would normally self-initiate antibiotics and increase airway clearance, thereby undertreating
 - Overestimating: the system may over detect small exacerbations where families would normally not initiate antibiotics and increase physiotherapy, thereby leading to increased utilisation of antibiotics, however increased airway clearance may benefit the patient without clinical harm.

Known potential benefits

- It is well known that earlier detection and aggressive treatment of pulmonary exacerbations leads to better outcomes in people with CF
- Increased and clearer pathways of communication with CF team
- Continuous rather than episodic care
- Increased participant understanding of what an exacerbation entails
- Symptom monitoring storage in EPIC to help inform traditional CF clinic reviews and improving in-clinic efficiency
- Ongoing symptom monitoring helping to guide ongoing treatment decisions

Assessment of potential risks and benefits

- Underestimating/overestimating pulmonary exacerbations in patients leading to changes in treatment
 - Utilisation of a survey based on a validated survey

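### Adverse event capture is tied to delivery of the intervention, so as written controls have no capture window and adverse events outside the compared outcomes lack a concurrent comparator

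*Protocol*

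**What the plan says.** Section 5 (Safety Monitoring and Reporting) opens with the only adverse event capture rule in the protocol. Events, serious or not, are "captured from the time of first administration of the intervention until conclusion of the intervention", and each is then followed until it resolves or stabilises. The sentence names no arm.

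The Design paragraph of the Trial Design section says what the intervention is: the trial compares usual care with an intervention arm, "with the intervention being the new remote symptom monitoring and automated treatment plan model of care". Section 4, under Usual Care, describes the other arm: "Participants in the control arm will receive usual which consists of quarterly CF clinic visits", with urgent visits when a family calls.

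Two places use a looser time frame. The synopsis says "Participants will be involved in the study for approximately 14 months, including the intervention period of 12 months". Section 1.3 says "Intervention and follow period for participants: 12 months". Neither is limited to one arm.

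Section 5 also lists the clinical risks that the sponsor foresees. Over-detection of small exacerbations is described as "thereby leading to increased utilisation of antibiotics". For under-detection, "the system may miss small exacerbations where families would normally self-initiate antibiotics and increase airway clearance, thereby undertreating".

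On data common to both arms, section 4 says "A follow up survey will be sent to both the intervention and control group at 3, 6 and 12 months".

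**The concern.** A capture window that opens when the intervention is first given has no opening date for a child who is never given it. If site staff follow the sentence as written, adverse events are recorded in the intervention arm only. Children with CF have adverse events in any 12-month period. Without the same record in controls, background events cannot be separated from effects of the new model of care.

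This matters because the system tells families, without prior clinician contact, to start an antibiotic and to change airway clearance or inhalation therapy. Section 2.2 states that no literature is known on automated plans in CF. The pilot is also meant to inform a full trial, whose designers would want a first look at tolerability in both arms.

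The capture window is a data-collection rule, and the protocol sets it. This is therefore a rule that is badly fixed, and not a detail left for an analysis plan.

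**Working it through.** No figure in the protocol is at stake, so the main check is of the text.

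**Step 1. Does the window apply to controls?**
- Start and end of capture (section 5): first administration and conclusion of the intervention.
- The intervention (Trial Design, Design paragraph): the remote monitoring and automated plan model.
- What controls receive (section 4, Usual Care): quarterly clinics and family-triggered urgent visits.
- Result: neither the start nor the end of the window occurs for a control. No other section gives a second window.

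**Step 2. What is collected in both arms anyway?**
- EPIC data (section 4, EPIC reports): admissions for pulmonary exacerbation, length of stay, CF outpatient appointments and contacts.
- Survey at 3, 6 and 12 months (section 4, Questionnaires): exacerbations, health economic data and trial burden. The survey form is an appendix that is not at hand, so this rests on the description in the text.
- Compared by arm in section 6: exacerbations, change in FEV1, admissions, hospital days, CFQ-R and EQ-5D-Y.
- Antibiotic usage: named in the synopsis and the objectives table among the outcomes compared between the groups.

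**Step 3. What is left without a comparator?**
- The foreseen over- and undertreatment of exacerbations bears on outcomes in step 2, so those harms keep a comparator.
- Non-serious events such as antibiotic side effects appear in none of the both-arm sources as described.
- Admissions for other causes are outside the EPIC list. This part is less certain, because the synopsis and section 6 speak of admissions without limiting the cause.

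**Step 4. The intervention arm.** Time between randomisation and first administration is outside the window, as are new events after the intervention ends. For a family that stops early, the end of the window is not clearly the 12-month point.

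**Step 5. Scale, if both arms were covered.** Inputs: a minimum of 30 participants (Trial Design, Sample) and balanced permuted blocks (Randomisation). No ratio is stated; 1:1 is assumed, giving 30 / 2 = 15 per arm.

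Zero-event bound, one-sided 95%: 1 − 0.05^(1/n) = 1 − 0.05^(1/15) = 0.181, or 18.1%.

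Power to compare two event proportions, two-sided 0.05, normal approximation: Φ[(|p2 − p1| − 1.96 × SE0) / SE1], where SE0 = √(2p̄(1 − p̄)/15), p̄ is the mean of p1 and p2, and SE1 = √([p1(1 − p1) + p2(1 − p2)]/15). The proportions are assumed, for illustration.

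| p1 vs p2 | Power |
|---|---|
| 10% vs 30% | 27% |
| 20% vs 40% | 22% |
| 20% vs 50% | 40% |
| 30% vs 60% | 37% |

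For the first row: SE0 = √(2 × 0.2 × 0.8 / 15) = 0.146, SE1 = √((0.09 + 0.21)/15) = 0.141, and Φ[(0.2 − 1.96 × 0.146)/0.141] = Φ(−0.61) = 0.27.

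**The case against.** The strongest reply is that the rule does not exclude controls. The synopsis and section 1.3 apply a 12-month intervention or follow-up period to participants in general, so the authors may have meant one 12-month window for everyone. That is plausible, and for this reason the point is that the window is undefined for controls. It is not shown that controls are deliberately left out. But neither of those places is the adverse event rule, and section 5 is not worded in their terms. If a common window is intended, one sentence settles it.

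A reader might infer that harms of automated plans cannot be compared with usual care at all. The documents do not support that. The clinical harms named in section 5 concern over- and undertreatment of exacerbations, and the related measures are outcomes compared between arms. Antibiotic usage has no entry of its own in section 6, but it is a listed between-group outcome and its analysis may be described elsewhere.

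A reader might also infer that the window opens only at the first automated plan, so that children who never trigger one contribute no time. That reading is weak. The intervention is defined as the whole model, and section 4 starts it with onboarding material and a baseline symptom survey.

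Finally, no objective or hypothesis in section 3.1 concerns adverse event rates, and with about 15 per arm no excess could be shown convincingly even with complete data. This stands as a limit on inference. It does not justify recording events in one arm only, because even a descriptive table needs both columns.

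**Conclusion.** The point holds in a limited form. As written, adverse event capture is anchored to something only the intervention arm receives, and controls have no defined window. The consequence falls on adverse events other than the outcomes already compared by arm: antibiotic side effects clearly, and admissions for other causes if the EPIC list is followed. Those events would have no concurrent comparator.

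The conclusion rests on the literal wording of section 5; a common window may have been intended. About 15 controls would be affected, if the minimum of 30 is split equally. At that size, power for the assumed differences of 20 to 30 percentage points is 22% to 40%, so the gain from correcting the rule is a fair description by arm and not a test. The primary feasibility and acceptability objectives are not affected.

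**What to change.** Replace the capture sentence in section 5 with one that states that adverse events are captured in both arms from randomisation to the 12-month assessment, whether or not the family continues with the intervention. Collect them in the same way in both arms: one identical item in the 3, 6 and 12 month survey that both arms already receive, and the same chart review. Report counts and person-time descriptively by arm.

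The cost is one protocol sentence, one survey item and slightly more data entry for controls. One limitation remains. The trial is not blinded and the intervention arm has more contact with the CF team, so events may still be noticed more readily there. The common survey item reduces that difference but does not remove it, and the report should say so.

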CF MDT will be sent a PICF (Appendix 6) describing the purpose of the trial and inviting them to participate in semi-structured interviews. Once consent has been gained, the PI will contact them to make a time for the semi-structured interview.

Randomisation:

Randomisation will occur after consent in signed and will be performed by a person independent to the study. A stratified randomization will be employed with the goal of ensuring balance between study arms by risk category employed by the RCH CF team. The randomisation schedule will be created by computer-generated random numbers, before the first participant has been recruited. The participant cohort will be stratified by child risk category (2 levels of category: 1 Very high risk & high risk and 2 Medium risk & low risk). Within each strata, permuted block randomisation will be used to ensure balance between the intervention and control group. A randomly generated sequence of block sizes containing 2, 4, or 6 participants will be used. This will help ensure balance in numbers between intervention and control groups, prevent potential confounders of risk category type impacting the measurement of outcomes, and prevent any predictability in intervention allocation[28]. The schedule will be held by an independent person, and allocation will not be

revealed prematurely to CI. Because of these procedures, the research team will be unable to predict which group the participant will be allocated to.

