- Increased burden of care to families by having to fill out the symptom surveys twice a week
 - Patient choice to fill out survey
- Increased workload for CF team without extra funding
 - Mostly automated system, relieving large burden on CF team
 - CF team involved in design of the intervention

6 Analysis:

STATISTICAL METHODS

Methods of analysis

Quantitative analysis:

Statistical analysis will be performed utilizing Statistical Package for the Social Sciences (SPSS). Descriptive statistics will be presented as mean (standard deviation, SD) or median (interquartile range, IQR). Categorical variables will be reported descriptively using frequency (n) and proportion (%).

Primary analysis:

1. To assess the **uptake and feasibility** of the remote monitoring and automated treatment plans
 - a. Total number of symptom surveys completed will be compared to total number of surveys expected and presented as a percentage.
 - b. Total number of tasks completed will be compared to expected number of tasks completed and presented as a percentage.
 - c. Number of contacts between CF team and family will be collated and compared between the intervention and control group using paired t tests or the non-parametric equivalents.

Secondary:

1. To understand **changes in outcome measures** over time between the two groups in children on highly effective modulators
 - Number of exacerbations detected
 - Total number of exacerbations per year will be calculated in each arm and presented descriptively. Comparison between groups will occur using t-tests or Chi squared test (or non-parametric alternatives as required)
 - Change in FEV₁
 - Data will be expressed as litres and percentage predicted. For each individual the FEV₁ at study entry will be compared to the FEV₁ at study completion, to determine the change in FEV₁. The average change in FEV₁ between the intervention and control group will then be compared using t-tests or Chi squared test (or non-parametric alternatives as required).
 - Number of admissions
 - Total number of admissions per year will be calculated in each arm and presented descriptively. Comparison between groups will occur using t-tests or Chi squared test (or non-parametric alternatives as required)
 - Hospital length of stay
 - Total number of hospital days per year will be calculated in each arm and presented descriptively. Comparison between groups will occur using t-tests or Chi squared test (or non-parametric alternatives as required)

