 - CFQ-R
 - Total score (mean and standard deviation) will be presented descriptively and comparison between groups will occur using t-tests or Chi squared test (or non-parametric alternatives as required)
 - EQ-5D-Y
 - Total score (mean and standard deviation) will be presented descriptively and comparison between groups will occur using t-tests or Chi squared test (or non-parametric alternatives as required)

2. To assess the **cost-effectiveness** of the remote monitoring and automated treatment plans compared to usual care by undertaking a health economic evaluation from both the perspective of the healthcare system and caregivers.
 - a. The cost of the new model will be estimated from the study protocol and budgets.
 - b. Difference in the patient's quality of life (EQ-5D-Y and CFQ-R) will be measured within the trial period for each arm and calculated using an area under the curve method.
 - c. Health service cost from hospital linked data along with patient costs will also be incorporated
 - d. Cost-effectiveness estimates of a cost per exacerbation avoided and cost per QALY for the new model compared with standard care will be generated for the trial period to justify the value of the new model of health monitoring.
 - e. Sensitivity analyses will be used to explore the variation in data. Wide cost confidence intervals are expected with a pilot study. The data collection will however inform acceptability and feasibility of economic data and contribute to the case or otherwise for a full trial.

Qualitative analysis:

Primary analysis:

1. To assess the **impact and acceptability** of the remote system monitoring and automated treatment plans on **family experience** (measured as experience of the program; acceptability of the program) compared to usual care;
2. To assess the **impact and acceptability** of the remote system monitoring and automated treatment plans on **CF MDT experience** (measured as experience of the program; acceptability of the program) compared to usual care.

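### One menu of tests for all secondary outcomes offers chi-squared where it cannot apply or can mislead, and leaves the quality-of-life baselines and the randomisation stratum unused

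*Protocol*

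**What the plan says.** Under the secondary analyses in section 6 of the protocol, the same choice of tests follows exacerbations, FEV₁, admissions, length of stay, CFQ-R and EQ-5D-Y.

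- **FEV₁.** Each child's value "at study entry will be compared to the FEV₁ at study completion, to determine the change in FEV₁". The average change "between the intervention and control group will then be compared using t-tests or Chi squared test (or non-parametric alternatives as required").
- **CFQ-R and EQ-5D-Y.** For each: "Total score (mean and standard deviation) will be presented descriptively and comparison between groups will occur using t-tests or Chi squared test", with the same non-parametric fallback. Neither change nor baseline is mentioned, although the study timeline in section 4 schedules both instruments at baseline and at 12 months. The objective above these analyses concerns how outcomes change over time.
- **Events.** Exacerbations, admissions and hospital days are summed by arm, for example "Total number of hospital days per year will be calculated in each arm and presented descriptively". The between-group comparison then uses the same menu.
- **Stratum.** The Randomisation section states: "The participant cohort will be stratified by child risk category" (two levels). None of the comparisons mentions it.
- **Size.** Under Sample: "we will aim to include a minimum of 30 participants in the study". No alpha, power, event rate or SD is given.

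**The concern.** A menu is harmless if every option on it is valid for every outcome it covers. Here one option is not. A chi-squared test compares counts or proportions, so it has no meaning for a mean change in litres or a mean questionnaire score. For events, the protocol forms arm totals and then offers chi-squared. A reader could put the two totals straight into that test, which counts four exacerbations in one child, or ten days of one admission, as independent observations.

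Separately, the quality-of-life comparison leaves out baseline scores that are already in hand, and no comparison uses the factor that the randomisation balanced.

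The Sample section says the outcome data are meant to feed sample-size calculations for later trials, and one hypothesis is that the new model detects more exacerbations. A spurious exacerbation signal, or an SD larger than the one a full trial would face, would carry over into that planning.

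**Working it through.** **Inputs.** From the protocol: at least 30 children; two arms; one stratification factor with two levels; 12 months of follow-up. Balanced blocks imply about 15 per arm ("Within each strata, permuted block randomisation will be used to ensure balance between the intervention and control group"). Assumed throughout, because the protocol gives no figures: two-sided 5% level, no dropout, and every event rate, dispersion and correlation below. There is no planned figure to reproduce; the 30 rests on precedent.

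**1. Chi-squared on two arm totals.** With equal arms the statistic is (T₁ − T₂)²/(T₁ + T₂). It is calibrated for a variance equal to the mean. If per-child counts have variance/mean ratio V, the true rejection rate under the null is about 2(1 − Φ(1.96/√V)). For negative binomial counts with mean m and dispersion k, V = 1 + km.

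| m | k | V | Formula | Simulated (20,000 trials) | Per-child t-test |
|---|---|---|---|---|---|
| 1 | 0 | 1 | 5.0% | 5.2% | 5.0% |
| 1 | 0.5 | 1.5 | 11.0% | 11.1% | 4.9% |
| 1 | 1 | 2 | 16.6% | 17.2% | 4.7% |
| 1 | 2 | 3 | 25.8% | 25.5% | 4.0% |
| 2 | 0.5 | 2 | 16.6% | 16.4% | 4.7% |
| 2 | 1 | 3 | 25.8% | 25.3% | 4.5% |
| 2 | 2 | 5 | 38.1% | 37.6% | 4.0% |

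So the range is about 11–38% for means 1–2 and dispersion 0.5–2, and about 5% with no overdispersion.

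Hospital days are worse because days come in runs. Take 20% of children admitted once, for 7–14 days with equal probability:

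- mean 0.2 × 10.5 = 2.1 days;
- variance 0.2 × (5.25 + 10.5²) − 2.1² = 23.1 − 4.41 = 18.69;
- V = 18.69/2.1 = 8.9, so the formula gives 51%.

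Simulation gives 54%, against 4.8% for a per-child t-test. With 0.3 admissions per child-year of 10 days each, simulation gives 57%.

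**2. Use of baseline.** With equal SDs and baseline-to-12-month correlation r, the variances relative to a final-score comparison are: final score 1, change score 2(1 − r), baseline-adjusted (ANCOVA) 1 − r².

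| r | Final score | Change | ANCOVA | ANCOVA v. final score | ANCOVA v. change |
|---|---|---|---|---|---|
| 0.5 | 1 | 1.00 | 0.75 | 25% lower | 25% lower |
| 0.6 | 1 | 0.80 | 0.64 | 36% lower | 20% lower |
| 0.8 | 1 | 0.40 | 0.36 | 64% lower | 10% lower |

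The comparison with the final score applies to CFQ-R and EQ-5D-Y; the comparison with change applies to FEV₁. Estimating the slope at N = 30 multiplies the ANCOVA variance by about 1 + 1/26 = 1.04. At r = 0.6 it becomes 0.64 × 1.04 = 0.67, still about a third below the final score.

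For planning: detecting 0.5 SD with 80% power takes 63 per arm on final scores, and 48 (r = 0.5) or 33 (r = 0.7) per arm with ANCOVA.

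Chance imbalance: the difference in baseline means has SD √(2/15) = 0.365 in SD units, so it exceeds 0.5 SD in 2(1 − Φ(0.5/0.365)) = 17% of trials.

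**3. Leaving out the stratum.** Simulated with balanced strata of 10 and 20 children, the unadjusted t-test rejects a true null in 4.5%, 3.2% and 1.6% of trials for stratum effects of 0.5, 1.0 and 1.5 SD. Adjusting restores about 5%.

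**The case against.** The strongest reply is that the menu need not be misused. The arm totals are described as a descriptive display, and the comparison is a separate sentence. The first-named test, the t-test, needs one value per child and holds its level. Chi-squared could be meant for the proportion of children with any event, where it also rejects about 5% under the null. This stands: a reader might infer that the plan ignores clustering of events, but the text only leaves that route open. It does not answer the defect in the wording, since the same sentence offers chi-squared for mean changes and mean scores, where no sensible use exists.

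A reader might also infer that baseline is ignored throughout. For FEV₁ that is wrong: it is analysed as change from entry, which is valid, and ANCOVA adds only a modest gain. For CFQ-R and EQ-5D-Y a final-score comparison is unbiased under randomisation, and its standard error already allows for chance imbalance. The loss is precision, and the analysis does not match an objective about change.

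Nor does omitting the stratum create false positives; its effect runs the other way. Covariates are often left to a statistical analysis plan, which is not at hand, so silence on the stratum alone would not be a finding. It is included because the comparison sentences must be rewritten anyway.

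Finally, these are secondary outcomes of a small pilot with no power claim. That limits the consequence.

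**Conclusion.** The point holds in limited form. The firm error is the wording that offers chi-squared for every secondary clinical outcome: it is inapplicable to FEV₁ change and the questionnaire scores, and unsafe on arm totals of recurrent events or days. If it were used on totals, false-positive rates of about 11–38% for counts and roughly 55% for hospital days would follow under the assumed rates, falling to about 5% if children did not differ in their underlying event rate. The documents give no event rates, so these sizes are illustrations.

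The unused baseline for CFQ-R and EQ-5D-Y costs precision (36% of variance at an assumed r = 0.6) and introduces no bias. The corresponding gain for FEV₁ is modest (20% at r = 0.6, 10% at r = 0.8). The unused stratum makes tests conservative. The change is worth making, mainly because these data are intended to plan a full trial.

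**What to change.** Replace the common menu with one method per outcome type:

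- **Chi-squared:** delete it except for binary outcomes, such as the proportion of children with at least one exacerbation.
- **FEV₁, CFQ-R, EQ-5D-Y:** a linear model of the 12-month value on arm, the child's baseline value and risk category.
- **Exacerbations, admissions, hospital days:** one rate per child (events or days over that child's follow-up time), preferably compared by a permutation or rank test stratified by risk category. A count model that allows overdispersion is an alternative if it fits at about 15 per arm. Arm totals can stay as a descriptive display.
- **Reporting:** give each between-group difference with a 95% confidence interval.

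The cost is analysis wording only. Baseline values and risk category are already collected. The linear models spend two degrees of freedom: with 30 children, 28 residual degrees of freedom in the t-test become 26.
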